4.1 Inclusion Criteria

1. Have been administered a GBCA \geq 30 days, but less than 10 years, prior with a confirmation lab result of elevated levels by 24 hour urine
2. Exhibiting \geq 3 of the following symptoms which must be present after having been administered a GBCA:
 - a. Cognitive disturbance

- b. Extremity pain
- c. Headache
- d. Chest wall pain
- e. Skin induration
- f. Skin hyperpigmentation
- g. Skin pain
- h. Arthralgia

4.2 Exclusion Criteria

1. Pregnant/lactating
2. Less than 18 years old
3. If there is no evidence of gadolinium (has to have shown previous demonstration of Gd by bone biopsy or urine analysis)
4. Known connective tissue disease such as Systemic Lupus Erythematosus and scleroderma
5. Severe hemochromatosis or Wilson's disease
6. Glomerular filtration rate (GFR) ≤ 60
7. Have not had an investigational drug within the past 30 days
8. Unable to give written consent
9. Multiple sclerosis
10. Chronic heart failure
11. Cirrosis of the liver

4.3 Subject Recruitment and Screening

Study subjects will be recruited as they seek us out from patient activist groups of gadolinium toxicity. In most cases it will be a first come first serve basis, but patients will also be prioritized based on levels of incapacitation by the gadolinium deposition disease.

Screening will include:

- 24-hour gadolinium urine
- Pain/QOL assessments
- Blood chemistries: calcium, zinc, manganese, magnesium, sodium, potassium, chloride, Creatinine, BUN, CO₂, Phosphorus, CBC/Diff, urinalysis, creatinine clearance.

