10	STUDY MONITORING, AUDITING, AND INSPECTING	17
10.1	STUDY MONITORING PLAN.....	17
10.2	AUDITING AND INSPECTING	17
11	ETHICAL CONSIDERATIONS	17
12	STUDY FINANCES	17
12.1	FUNDING SOURCE.....	17
12.2	CONFLICT OF INTEREST	17
13	PUBLICATION PLAN	18
14	REFERENCES	18
15	APPENDICES (.....	18

List of Abbreviations

DTPA—Diethylene Triamine Penta-acetic Acid

Gd—Gadolinium

GBCA—Gadolinium Based Contrast Agent

MRI—Magnetic Resonance Imaging

Study Summary

Title	INVESTIGATOR-INITIATED INVESTIGATIONAL NEW DRUG (IND) APPLICATION TO STUDY THE EFFECTS OF INTRAVENOUSLY ADMINISTERED CA-DTPA AND ZN-DTPA TO TREAT PATIENTS WITH GADOLINIUM DEPOSITION DISEASE
Short Title	Ca/Zn DTPA for GDD
Protocol Number	GDD-001
Phase	Feasibility study
Methodology	Open label, non-randomization
Study Duration	1 year
Study Center(s)	Single center
Objectives	To see an increase in the elimination of Gd as measured by analysis of 24 hour urine collections.
Number of Subjects	20
Diagnosis and Main Inclusion Criteria	Gadolinium Deposition Disease (GDD)— *Symptoms of pain, depressed levels of consciousness, and skin induration post administration of a GBCA as well as elevated levels of gadolinium in 24 hr urine, greater than 30 days post administration of a GBCA
Study Product, Dose, Route, Regimen	Ca –DTPA (0.5 gm) administered IV push over 1 minute at the beginning of infusion, along with normal saline (over a 90 minute period), ending with another 0.5 gm DTPA dose with 10 minutes left of saline infusion. This will be followed the next day with Zn-DTPA (0.5 gm) administered IV push over 1 minute with normal saline (over a 90 minute period), ending with another 0.5 gm DTPA dose with 10 minutes left of saline infusion. A total of 1 gm of DTPA is administered at each treatment. This sequence will be administered 3 times, approximately 1 month apart.
Duration of administration	3 months
Reference therapy	No treatments established for this condition
Statistical Methodology	R, a language and environment for statistical computing (R Core Team, Vienna, Austria), will be used for all statistical computing. Statistical significance will be defined as p value less than 0.05.

1 Introduction

[figure not shown]

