3.2 Primary Study Endpoints

To observe a reduction or elimination of symptoms caused by gadolinium deposition after administration of a GBCA.

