5.3 Method for Assigning Subjects to Treatment Groups

No randomization will be used. All patient subjects will receive the same treatment therapy.

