5.9.4 Return or Destruction of Study Drug

At the completion of the study, there will be a final reconciliation of drug shipped, drug consumed, and drug remaining. This reconciliation will be logged on the drug reconciliation form, signed and dated. Any discrepancies noted will be investigated, resolved, and documented prior to return or destruction of unused study drug. Drug destroyed on site will be documented in the study files.

6 Study Procedures

6.1 **Visit 0-** The patient will be seen and evaluated by a UNC clinician regarding symptoms, assessments, a physical exam, a medication history and lab values up to one week prior to anticipated therapy start date. After agreeing to participate in the study, a coordinator will obtain informed consent signatures and the patient will be instructed to collect a 24-hour urine so that gadolinium can be measured for pre-treatment values.

6.2 **Visit 1-** The patient will come for infusion chelation therapy with Ca-DTPA to be done in the Clinical and Translational Research Center. Patient will void and have a baseline blood pressure taken before start of treatment. A urine pregnancy test will be performed if the subject is a woman of child-bearing potential. Blood samples will be collected by phlebotomy trained staff at the Clinical & Translational Research Center (CTRC) at UNC Memorial hospital. Patient blood samples will be obtained just prior to intravenous administration of Ca-DTPA or Zn-DTPA. The IV will be placed by nursing staff, and the infusion of normal saline will begin. The first injection of Ca-DTPA is performed by the investigator, or one of the co-investigators. Five (5) minutes post injection of Ca-DTPA another blood

pressure will be taken. Saline will continue for another 80 minutes, and the second injection of Ca-DTPA will be given by an investigator, followed by the last 10 minutes of saline infusion. IV will be discontinued, vitals checked, and patient will be discharged home. Patient will begin 24-hour urine collection once the infusion is started. They will be instructed to drink plenty of fluids. Analog pain scale sheets will be given to the subject to fill out starting with day 1 through day 6 post treatment, which will be returned on the day 7 visit. Urine is to be brought in on 2nd day of therapy.

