7.1 Sample Size Determination

Twenty subjects will be evaluated to determine the safety profile of chelation in this setting and to provide information on potential endpoints for future studies in this area. The distributions of urinary measures of Gd excretion as well as for pain and quality of life will be evaluated at baseline and after each treatment, as will the differences in these measures between baseline and each treatment.

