7.2 Statistical Methods

Changes between baseline and each treatment will be evaluated for direction and magnitude. Although the goal is estimation of effect size and variation, statistical tests for changes pre/post treatment will be evaluated to understand the pre/post changes toward development of a future trial. These tests will evaluate the null hypothesis of no change in urine measures or symptoms (via questionnaire). If the changes in measures are normally distributed, then paired t-tests will be used. However, it is more likely that the data will not be normally distributed and that Wilcoxon signed-rank tests will be need. For any nominal (yes/no) questionnaire data, a McNemar's or sign test will be used for the paired contingency table. Since these tests will likely be used in future studies, direction of effect measures (differences) and ranges of estimates (confidence intervals) will provide information on what to expect in testing and analyzing more individuals

Subject Population(s) for Analysis

All-treated population: All subjects consenting to study will be treated with the same therapy, receiving at least one dose of study drug.

8 Safety and Adverse Events

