12.2 Conflict of Interest

Any investigator who has a conflict of interest with this study (patent ownership, royalties, or financial gain greater than the minimum allowable by their institution, etc.) must have the conflict reviewed by a properly constituted Conflict of Interest Committee with a Committee-sanctioned conflict management plan that has been reviewed and approved by the study sponsor prior to participation in this study. All University of UNC investigators will follow the University conflict of interest policy.

13 Publication Plan

Neither the complete nor any part of the results of the study carried out under this protocol, nor any of the information provided by the sponsor for the purposes of performing the study, will be published or passed on to any third party without the consent of the study sponsor. Any investigator involved with this study is obligated to provide the sponsor with complete test results and all data derived from the study.

14 References

1. Sieber MA1, Lengsfeld P, Walter J, Schirmer H, Frenzel T, Siegmund F, Weinmann HJ, Pietsch H., Gadolinium-based contrast agents and their potential role in the pathogenesis of nephrogenic systemic fibrosis: the role of excess ligand. *J Magn Reson Imaging*. 2008 May;27(5):955-62 doi: 10.1002/jmri.21368

15 Appendices

- A. Table of Events
- B. Visual Analog Pain Scale
- C. Quality of Life scale
- D. Copy of Consent Form

Time and Events Table:

	Pre-treatment Visit 0	V 1 Day 1	V 2 Day 2	V 3 Day 3	V 4 Day 7	V 5 Day 1 Mo 2	V 6 Day 2 Mo 2	V 7 Day 3 Mo 2	V 8 Day 7 Mo 2	V 9 Day 1 Mo 3	V10 Day 2 Mo 3	V 11 Day 3 Mo 3	V 12 Day 7 Mo 3	V 13-14 Mo 6 & 12
Physical Assessments	X				X				X				X	
Labs	X	X ^c		X		X ^c		X		X ^c		X		
24 hr urine gd	X	X ^a	X ^a			X ^a	X ^a			X ^a	X ^a			
Pain/QOL questionnaire	X				X ^e				X ^e				X ^e	X ^d
IV Ca-DTPA therapy		X				X				X				
IV Zn-DTPA therapy			X				X				X			

- a. Patients will begin 24hr urine collection immediately following therapy
- b. Assessments may be done by phone when patient lives greater than 3 hours away
- c. Urine pregnancy testing will be done on day one of therapy for WCBP

- d. Patients will be called to collect pain and QOL data at months 6 and 12
- e. Pain/QOL questionnaires will be filled out days 1-6 and returned day 7

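### Symptom change appears to rest on one pre-treatment score from the screening visit, with no run-in or control, so regression to the mean can add to apparent improvement by an amount the plan cannot separate

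*Combined protocol and SAP*

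**What the plan says.** - **Endpoint and test.** Section 3.2 gives the primary endpoint as "To observe a reduction or elimination of symptoms caused by gadolinium deposition after administration of a GBCA". Section 2 ranks symptoms as a secondary objective, so the two sections differ. Section 7.2 states "Changes between baseline and each treatment will be evaluated for direction and magnitude", with paired tests of no change. The Study Summary adds "Statistical significance will be defined as p value less than 0.05". There is no comparison group. Section 5.3 reads "No randomization will be used. All patient subjects will receive the same treatment therapy".
- **Baseline.** Section 4.3 lists Pain/QOL among the screening items. The Time and Events Table marks it once before treatment, at V0. Section 3.1 makes the baseline visit the one that decides eligibility. Section 6.1 has the clinician review symptoms, history and "lab values up to one week prior to anticipated therapy start date", which I read as placing V0 within a week before V1. No run-in or second pre-treatment score is described. The table shows no Pain/QOL mark before infusion at V5 or V9, so V0 appears to be the reference for all three rounds.
- **Who enters.** Under section 4.3 patients approach the site through activist groups and are mostly taken in order of arrival, but "patients will also be prioritized based on levels of incapacitation by the gadolinium deposition disease". How incapacitation is judged, and for how many patients it decides entry, is not stated. Section 4.1 requires at least three of eight symptoms and sets no pain or QOL threshold.
- **Follow-up.** Table footnote e says "Pain/QOL questionnaires will be filled out days 1-6 and returned day 7". Section 6.2 describes the day 1 to 6 sheets as pain scales only. Sections 3.1 and 6.5 also describe an assessment at the one-week visit. Months 6 and 12 are single calls. Section 7.2 does not say how the daily forms become one value.

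**The concern.** With no control arm, the V0 score carries the whole symptom inference, and any error in it enters the change score for every round. If some patients come forward, or are moved forward, during a bad spell, their later scores will tend to drift back towards their usual level without any drug effect. The plan has no means of telling that drift from benefit. Section 7.2 says the goal is to estimate effect size and variation for a future trial, so both a shifted mean and an inflated SD would be carried into that trial's design.

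**Working it through.** The plan gives no figure to reproduce. Section 7.1 says "Twenty subjects will be evaluated to determine the safety profile of chelation in this setting" and supplies no SD, effect size, power or test-retest value.

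**Inputs from the documents:** n = 20, one arm, alpha 0.05 (taken as two-sided, since the plan does not say), one V0 score, daily forms on days 1 to 6 after each round, V0 up to a week before V1.

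**Assumptions (not in the documents):** ICC between occasions 0.6 to 0.8 (0.5 to 0.9 in the simulation); a share p of patients selected on a temporarily raised V0 score; those patients on average z = 1 SD high; for conversion to points, a 0-10 scale with SD 2.5.

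**1. Expected apparent fall with no drug effect** = p × (1 − ICC) × z, in SDs of a single score.

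| Selection | ICC 0.8 | ICC 0.6 | Points at SD 2.5 |
|---|---|---|---|
| None, or on stable severity only | 0 | 0 | 0 |
| p = 0.25 | 0.25 × 0.2 = 0.05 | 0.25 × 0.4 = 0.10 | about 0.1 to 0.25 |
| p = 1 | 0.2 | 0.4 | 0.5 to 1.0 |

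An average of 1 SD high means taking roughly the worst 38% on the V0 score, so the last row is a near-extreme case.

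**2. False significant improvement** (simulation, n = 20, no effect, paired t-test, 4,000 runs per setting; nominal 2.5% in the improving direction). Follow-up is the mean of six forms. Selected patients are the worse half on V0. Non-stable variance is split equally between a week-level and a day-level part.

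| Selection on V0 score | ICC 0.5 | ICC 0.7 | ICC 0.9 |
|---|---|---|---|
| None | 2.5% | 2.5% | 2.6% |
| All, on stable severity only | 2.6% | 2.6% | 2.2% |
| A quarter of patients | 6% | 5% | 4% |
| Half | 14% | 10% | 6% |
| All | 54% | 35% | 14% |

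In the last row the simulated mean fall is 0.39 / 0.24 / 0.08 SD. The truncated-normal formula, (1 − ICC) × 0.399/0.5, gives 0.40 / 0.24 / 0.08.

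**3. One form against six.** With no selection the mean change is 0.00 SD whether follow-up is one form or six. With all patients selected at ICC 0.5 the mean fall is 0.39 SD either way; only the rejection rate moves, from 44% to 54%, because the six-form mean is less noisy.

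**4. Noise from the one-day baseline.** With m baseline days, six follow-up days, independent daily errors and the same true change in everyone, the change variance is (1 − ICC)(1/m + 1/6) SD².
- m = 1: (1 − ICC) × 1.167, giving a change SD of 0.68 at ICC 0.6 and 0.48 at ICC 0.8.
- m = 6: (1 − ICC) × 0.333, giving 0.37 and 0.26. The SD is lower by 1 − √(0.333/1.167) = 47%.
- If half the transient variance is shared across a week, the multipliers are 1 + 0.583 = 1.583 and 0.583 + 0.583 = 1.167, and the reduction is 1 − √(1.167/1.583) = 14%.

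Reliability of a six-day baseline with independent daily errors (Spearman-Brown): 6 × 0.6/(1 + 5 × 0.6) = 0.90 and 6 × 0.8/(1 + 5 × 0.8) = 0.96, against 0.6 and 0.8 for one day.

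**5. What a run-in removes.** With independent daily errors, a run-in mean that excludes V0 carries none of the selection error. If half the transient variance is shared across that week, it still carries half: 0.1 to 0.2 SD of the 0.2 to 0.4 SD in the p = 1 case.

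**The case against.** The best defence is that selection on the V0 score is not documented. Most enrolment is in order of arrival. Prioritisation sits under recruitment, section 6.1 already has a planned start date at V0, and section 11 requires consent before any study procedure, so the V0 form may well follow the decision to offer a place. Incapacitation may mean lasting disability, in which case no shift is expected. The one-week assessment in sections 3.1 and 6.5 may already give a single post-treatment score comparable with V0. This is a 20-patient feasibility study, section 2 makes symptoms secondary, and the urine measures do not use this score.

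Most of that stands, and it limits the size. It does not remove the point. Self-referral and the three-symptom rule apply to every patient, though the documents quantify neither. A priority decision made shortly before V0, during a bad spell that is still running, would leave part of the same error in the V0 score. Feasibility status lowers the weight of the p-values, but the effect size and its SD are the intended product. The noise argument needs no selection at all.

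A reader might infer that six follow-up forms against one baseline form builds in improvement. It does not: the mean is unmoved, and averaging six forms reduces noise. A reader might also infer that the best of the six days will be used. The plan states no such rule; the missing summary is a gap in detail, not evidence of a favourable choice.

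**Conclusion.** The point holds in a limited form. Symptom change is uncontrolled and appears to rest on a single V0 score, an inference from the one pre-treatment mark in the events table. Regression to the mean can contribute to apparent improvement: near zero if priority tracks stable severity, about 0.05 to 0.1 SD if a quarter of patients are selected about 1 SD high, and 0.2 to 0.4 SD only if all are, at an assumed ICC of 0.6 to 0.8. It is tempting to conclude that patients are generally enrolled at their worst and that a fall of half to one point should be expected from this alone. The documents do not support that, because they make order of arrival the main rule and never tie priority to the V0 score. Independently of selection, replacing the one-day baseline with six days would lower the SD of the change by about 14% to 47%, depending on how far daily errors are shared within a week. This is a worthwhile, inexpensive improvement rather than a fatal flaw.

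**What to change.** - **Section 6.1:** hand out the same daily sheets at V0, to be completed each day until V1, the last one before infusion.
- **Section 7.2, baseline:** define it as the mean of these run-in days, excluding the V0 score. Report the V0-to-run-in change as untreated drift beside the post-treatment change.
- **Section 7.2, follow-up:** prespecify one post-round summary that cannot pick a favourable day, such as the mean of days 1 to 6. Show the daily scores with it, because section 8.1 anticipates a possible flare of symptoms that such a mean would absorb. State how the one-week assessment and the month 6 and 12 calls are compared with baseline, and whether the daily sheets cover pain only or Pain/QOL.

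The cost is up to six extra sheets per patient, on forms already in the protocol, plus wording in two sections. V0 should fall several days before V1. Patients with a short gap, for example those who combine the two visits in one trip, will contribute fewer run-in days. Regression is only partly removed if flares outlast the run-in.

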4.4 Early Withdrawal of Subjects

Patients may remove themselves from the study at any time for any reason. The investigators may remove patients from the study for any reason, such as non-compliance, or patient safety concerns.

4.4.1 When and How to Withdraw Subjects

Study subjects will be withdrawn from the study if they experience any known or unknown severe adverse event following administration of either Ca-DTPA or Zn-DTPA. Treatment will be discontinued immediately following any severe adverse event.

4.4.2 Data Collection and Follow-up for Withdrawn Subjects

The same labs done at screening will be collected, and a follow up phone call will be made one week after the event.

5 Study Drug

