5.5 Subject Compliance Monitoring

Subjects are treated and discharged from the clinic. They will be instructed to drink plenty of fluids, and collect urine for the following 24 hours to be returned the following day. Subjects will also have blood chemistries drawn the day following the second infusion for monitoring. Subject treatment will discontinue if they do not collect the 24 hour urine sample for testing following the infusion therapy, or refuse blood chemistry monitoring.

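### Section 4.4.2 requires no pain/QOL form after withdrawal, so later symptom analyses could omit withdrawn subjects despite the all-treated label

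*Combined protocol and SAP*

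**What the plan says.** Section 4.4.2 is the only place that sets out what is collected after withdrawal: "The same labs done at screening will be collected, and a follow up phone call will be made one week after the event". The content of the call is not described. Section 4.3 lists "Pain/QOL assessments" as a screening item separate from the blood chemistries, so a reference to labs does not naturally include it.

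There are several ways to stop:

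- Section 4.4.1: "Study subjects will be withdrawn from the study if they experience any known or unknown severe adverse event" after either drug.
- Section 8.4 also withdraws subjects for severe events (grade 3 or 4), but only those it calls unknown. It separately discontinues subjects with Grade 3 hypocalcemia from the study.
- Section 4.4 lets patients leave at any time and adds: "The investigators may remove patients from the study for any reason, such as non-compliance, or patient safety concerns".
- Section 5.5: "Subject treatment will discontinue if they do not collect the 24 hour urine sample for testing following the infusion therapy". This sentence concerns treatment and does not say whether the subject stays in the study.

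Symptom reduction is the primary endpoint in section 3.2 and a secondary objective in section 2. Section 7.2 analyses change from baseline to each treatment with paired tests. Its population is all-treated: "All subjects consenting to study will be treated with the same therapy, receiving at least one dose of study drug". It gives no rule for missing values. Section 6.14 adds phone calls at months 6 and 12 and does not say whether withdrawn subjects receive them.

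**The concern.** A paired test uses only subjects with both values. If no scaled symptom measure is taken after withdrawal, a subject withdrawn in round 1 has no value for round 2, round 3 or the long-term calls, and the all-treated label cannot supply one. Missing data at later timepoints would then accumulate from round to round.

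The loss may be related to the outcome. Section 8.1 lists a possible flare of current symptoms among the expected adverse events. Under section 4.4.1 a severe flare could be both a worsening of the endpoint and a reason to leave. If subjects who worsen leave more often than the others, the remaining subjects show too favourable a change, and there is no control arm to reveal it. The plan's stated use of these results is to estimate effect sizes and their variation for a future trial, so the distortion would carry over into that design.

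**Working it through.** **Stated figures.** The plan gives no withdrawal rate, effect size, SD or power, so there is no figure to reproduce. Two inputs come from the documents:

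- N = 20 (section 7.1: "Twenty subjects will be evaluated to determine the safety profile of chelation in this setting").
- The significance level (Study Summary: "Statistical significance will be defined as p value less than 0.05"). Sidedness is not stated; two-sided is assumed.

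Everything else below is an assumption, used only to show a range.

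**Which values are at risk.** Pain sheets for days 1 to 6 are handed out at Visits 1, 5 and 9 (sections 6.2, 6.6 and 6.10). A subject withdrawn after a round-1 infusion already holds the round-1 sheets, so round 1 is less affected. Their return is planned for the day-7 visit, which section 4.4.2 replaces with a call. Nothing provides for forms at the times of Visits 8 and 12.

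**Illustration on the pain scale.** Assume those who stay change by -10 mm and those withdrawn by +20 mm. Those who stay show -10 mm whatever the number withdrawn. The all-treated mean is:

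- 2 withdrawn: (18 × -10 + 2 × 20)/20 = -7 mm
- 4 withdrawn: (16 × -10 + 4 × 20)/20 = -4 mm
- 6 withdrawn: (14 × -10 + 6 × 20)/20 = -1 mm

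**The same in SD units.** Let w be the number withdrawn and D the mean difference in change between those who stay and those withdrawn, with SD 1 within each group. If only those who stay are analysed, bias = (w/20) × D. The 95% half-width is t(0.975, n-1)/√n with n = 20 - w; for n = 20 it is 0.47 SD. The last column gives the simulated chance of a significant benefit when the true all-treated mean change is zero (paired t, 10,000 runs; Wilcoxon in brackets, 3,000 runs). The nominal value in that direction is 2.5%.

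| w | n | Half-width (SD) | D (SD) | Bias (SD) | False benefit |
|---|---|---|---|---|---|
| 2 | 18 | 0.50 | 0.5 | 0.05 | 3.8% (3.5%) |
| 2 | 18 | 0.50 | 1.0 | 0.10 | 6.1% (5.0%) |
| 4 | 16 | 0.53 | 0.5 | 0.10 | 5.3% (4.9%) |
| 4 | 16 | 0.53 | 1.0 | 0.20 | 11.4% (10.2%) |
| 6 | 14 | 0.58 | 0.5 | 0.15 | 7.6% (8.0%) |
| 6 | 14 | 0.58 | 1.0 | 0.30 | 18.3% (17.0%) |
| 8 | 12 | 0.64 | 0.5 | 0.20 | 9.7% (8.4%) |
| 8 | 12 | 0.64 | 1.0 | 0.40 | 24.2% (21.1%) |

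**Would a single zero-change analysis be enough?** With 4 withdrawn, counting each as unchanged gives (16 × -10 + 4 × 0)/20 = -8 mm, against -4 mm in the illustration. With 6 it gives (14 × -10 + 6 × 0)/20 = -7 mm, against -1 mm. Zero change under-corrects when the withdrawn subjects have worsened, so a worsening scenario is needed as well. With 4 withdrawn at an assumed +10 mm the result is (16 × -10 + 4 × 10)/20 = -6 mm; at +20 mm it is -4 mm.

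**The case against.** A reader might infer that all later results describe only those who tolerated and complied with treatment. The documents do not support that. A missed urine collection stops treatment under section 5.5, not expressly study participation. The month 6 and 12 calls go to subjects without being limited to completers. Subjects with non-severe events stay in. What stands is that the plan is silent on these points.

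A reader might also infer that a severe flare always leads to withdrawal. Section 4.4.1 points that way, but section 8.4 speaks only of unknown severe events, and flare is an expected one. The two passages conflict, so the link is possible and not established. Nothing in the documents ties hypocalcemia or a missed urine sample to symptom outcome.

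Worsening is not wholly unrecorded. Section 8.2 requires questioning about adverse events at every contact, which includes the one-week call, and section 8.1 treats a worsening pre-existing condition as an adverse event. This preserves knowledge that a subject worsened, but not a score that can enter the paired analysis.

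Withdrawals may be few. Section 1.4 reports minor transient effects in 12 of 485 treated workers and no serious effects, although in a different population. Subjects may also leave for reasons unrelated to symptoms, or because they feel better. In every assumed case above the bias is smaller than the confidence interval's half-width. Finally, this is a feasibility study without a confirmatory claim. That lowers the stakes but does not remove them, because estimation is its stated goal.

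**Conclusion.** The gap is real: no scaled symptom measure is required after withdrawal, there is no missing-data rule, and stopping treatment is not separated from leaving the study. The paired symptom analyses after rounds 2 and 3 and at months 6 and 12 could therefore omit withdrawn subjects; round 1 is less exposed. The estimate could be biased towards benefit.

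Neither the direction nor the size can be established from the documents. With 2 to 8 of 20 withdrawn and a gap of 0.5 to 1.0 SD, the bias runs from 0.05 to 0.40 SD; with no gap it is zero. A reader might conclude that the reported effect will be too favourable. That goes too far, because it assumes who leaves and why.

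**What to change.** **Section 4.4.2.** State that every subject who received at least one dose and agrees to continued follow-up completes the existing pain/QOL forms, by phone if needed, whether or not treatment was stopped. The times are the one-week call, the calendar times of Visits 8 and 12, and months 6 and 12. Agreement is needed because section 4.4 lets patients leave at will and section 9.1 lets them revoke authorization. Say in sections 4.4 and 5.5 which events end treatment only and which end study participation.

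**Section 7.2.** Analyse all treated subjects and report the number contributing at each timepoint. Add two sensitivity analyses for withdrawn subjects without data: one counting them as no improvement, one counting them as worsened by an amount or range set in advance.

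**Sections 4.4.1 and 8.4.** Reconcile the two descriptions of which severe events lead to withdrawal. This is a clinical decision for the sponsor and the investigator; the statistical need is only that there be one rule.

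**Cost.** A few extra forms or calls and a small sensitivity table. Phone follow-up is already provided for in sections 6.5, 6.13 and 6.14. The estimate may become less favourable. Scores not collected at the time cannot be recovered later.
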